5.3.5.2 Clinical Protocol**8.3.9. Follow-up of Unresolved Adverse Events**

All adverse events should be followed until they are resolved or the Investigator assesses them as chronic or stable. Any increase or decrease in adverse event grade should be recorded as a new adverse event.

All serious and those non-serious events assessed by the Investigator as possibly related to the investigational medication/product should continue to be followed even after the patient's participation in the trial is over. Such events should be followed until they resolve or until the Investigator assesses them as "chronic" or "stable." The event should also be documented on the adverse event CRF.

8.4. Safety Monitoring

The TRACON Clinical Team will monitor safety throughout the study via the following activities:

- Surveillance for SAEs according to regulatory guidelines
- Routine monitoring of non-serious adverse experiences as they are recorded in the case report forms and the source documents at study sites
- A formally chartered TRACON in-house Safety Review Team that includes, among other staff, two physicians
- A formally chartered external Safety Review Team that includes three physicians
- Periodic teleconferences with the Principal Investigators to share experiences and ensure communication
- Toxicity information that may affect the treatment of patients on this study will be promptly communicated in writing to all participating clinical sites and institutions participating in this clinical trial.

5.3.5.2 Clinical Protocol**9. OTHER ASSESSMENTS****9.1. Other Laboratory Assessments****9.1.1. Pharmacokinetics**

Samples will be sent to Fisher BioServices ([name]) for storage. See separate laboratory manual for specific collection, storage and shipping information.

9.1.1.1. TRC105 Peak and Trough Concentration (Phase 1b dose levels -1, 1, 2 and expanded cohort 1 and angiosarcoma cohort 2)

A 5 mL blood sample will be collected prior to dosing with TRC105 on the days indicated within the Schedule of Assessments (Table 4 and Table 7).

A 5 mL blood sample will be collected within 10 minutes following each TRC105 infusion on the days indicated within the Schedule of Assessments (Table 4 and Table 7).

Samples will be separated and stored at approximately -70 °C for shipment to third party laboratory. See separate laboratory guide for further collection and shipment information.

9.1.1.2. TRC105 and Pazopanib Trough Concentration (Phase 1b dose levels 3, expanded cohort 2 and Phase 2 including angiosarcoma cohort 1)

A 5 mL blood sample each for TRC105 and pazopanib pharmacokinetics to be collected at the time-points indicated in the Schedule of Assessments (Table 5, Table 6 and Table 7), prior to starting the TRC105 infusion and prior to pazopanib dosing. Samples will be stored at approximately -70°C. Samples will be batch shipped as indicated in the laboratory manual to a third-party laboratory. See separate laboratory guide for further collection and shipment information. Additional PK samples may also be collected at the time of unexpected clinical events.

9.1.2. TRC105 Immunogenicity

Samples will be sent to Fisher BioServices ([name]). See separate laboratory manual for specific collection, storage and shipping information.

Anti-product antibody concentrations will be measured using validated ELISA methods at the time points specified in the Schedule of Assessments ((Table 4, Table 5, Table 6 and Table 7) in all patients. Anti-product antibody concentrations will be evaluated in the context of pharmacokinetic parameters and AE profiles. Samples will be separated and stored at approximately -70 °C for shipment to Fisher BioServices. See separate laboratory guide for further collection and shipment information.

9.1.3. Protein Biomarkers

One 10mL purple top (K₂EDTA) tube of blood will be collected on the days indicated within the Schedule of Assessments (Table 4, Table 5, Table 6 and Table 7). Samples will be stored at approximately -70 °C and shipped to Fisher BioServices Inc. ([name]) for storage until the time of analysis. Duke University Medical Center will analyze plasma for several biomarkers including but not limited to VEGF, VEGF-R2, PIGF and sCD105

5.3.5.2 Clinical Protocol

(Phase 1 Biomarker Laboratory, Duke University Medical Center, [name]). Please see the separate laboratory guide for further collection and shipment information.

9.1.4. Archival Tumor Specimens

Archival specimens (formalin-fixed, paraffin-embedded) of the primary cancer and/or metastatic cancer specimen for each study participant will be obtained. It is preferable that the entire paraffin block be submitted, but if this is not feasible, then at least 20 unstained slides are requested for immunohistochemical analysis (sections of ~ 5 microns are preferred).

Samples will be stored at room temperature and shipped to Fisher BioServices Inc. ([name]) for storage until the time of analysis. See separate laboratory guide for further collection and shipment information.

5.3.5.2 Clinical Protocol

10. STATISTICS

10.1. Statistical Design/Sample Size

10.1.1. Phase 1b Statistical Design/Sample Size

The number of patients to be enrolled in this study will depend upon the observed safety profile, which will determine the number of patients per dose level and the number of dose escalations. It is anticipated that up to 30 patients will be enrolled in the phase 1b portion of the study.

The probability of escalation to the next higher dose for each underlying true DLT rate is shown in Table 17. For example, at a dose level with a true DLT rate of 5%, there is a greater than 95% probability of escalating. Conversely, for a dose level with a true DLT rate of 70%, the probability of escalating is < 5%.

Table 17: Probability of Escalation to the Next Dose for Each True Underlying DLT Rate at a Dose Level

True Underlying DLT Rate	5%	10%	20%	30%	40%	50%	60%	70%	80%	90%
Probability of Escalating Dose	0.97	0.91	0.71	0.49	0.31	0.17	0.08	0.03	0.01	0.001

The probability of failing to observe DLT in a sample size of 3 or 6 patients given various true underlying DLT rates is shown in Table 18. For example, with 6 patients, the probability of failing to observe DLT occurring at least 40% of the time is less than 5%.

Table 18: Probability of Failing to Observe True Underlying DLT Rate at a Dose Level

True Underlying DLT Rate	5%	10%	20%	30%	40%	50%	60%	70%	80%	90%
Probability of Failing to Observe Toxicity if N = 3	0.86	0.73	0.51	0.34	0.22	0.13	.0064	0.027	0.008	0.001
Probability of Failing to Observe Toxicity if N = 6	0.74	0.53	0.26	0.12	0.047	0.016	0.0041	<0.001	<0.001	<0.001

The estimated MTD is the highest tested dose level with a DLT rate < 33% in at least 6 DLT evaluable patients.

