5.3.5.2 Clinical Protocol

Probability of Failing to Observe True Underlying DLT Rate at a Dose Level

True Underlying DLT Rate	5%	10%	20%	30%	40%	50%	60%	70%	80%	90%
Probability of Failing to Observe Toxicity, N = 3	0.86	0.73	0.51	0.34	0.22	0.13	0.006	0.027	0.008	0.001
Probability of Failing to Observe Toxicity, N = 6	0.74	0.53	0.26	0.12	0.05	0.016	0.004	<0.001	<0.001	<0.001

Phase 2:

Primary analysis:

The primary analysis will test the null hypothesis that the median PFS is equal to 4.6 months. The time-to-event distribution for PFS will be estimated using the Kaplan-Meier method and the analysis will be based on the two-sided 90% confidence interval for the median (equivalent to the use of a one-sided test at the $\alpha=0.05$ level of significance).

An additional phase 2 cohort of up to 13 patients with angiosarcoma will be enrolled (angiosarcoma cohort 1). Assuming a 15% response rate by RECIST with pazopanib alone, 5 responders with TRC105 alone will provide >90% confidence that the true response rate is >15%.

A second additional phase 2 cohort of up to 13 patients with angiosarcoma will be enrolled (angiosarcoma cohort 2). Assuming a 15% response rate by RECIST with pazopanib alone, 5 responders with TRC105 in combination with pazopanib will provide >90% confidence that the true response rate is >15%.

Sample size justification:

Assuming a true median PFS of 4.6 months, a 9-month accrual period, a 6-month follow-up period, and based on the use of a one-sided test at the $\alpha=0.05$ level of significance, a sample size of 63 patients will provide 86% power to detect a 50% increase in the median PFS (i.e., a median of 6.9 months). For the angiosarcoma cohorts, the two-sided exact 90% binomial with 5 of 13 responders is 16.57% and 64.52%.

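### Table 18 and the synopsis misprint the chance of no DLT in three patients at a 60% true rate: .0064 and 0.006 should be 0.064

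*Combined protocol and SAP*

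**What the plan says.** Section 10.1.1 of the protocol gives two tables of operating characteristics for the 3+3 phase. Table 17 gives the probability of escalating at each true DLT rate. Table 18 gives the chance of missing toxicity altogether: "The probability of failing to observe DLT in a sample size of 3 or 6 patients given various true underlying DLT rates is shown in" that table. Its first row is "Probability of Failing to Observe Toxicity if N = 3". At true rates of 50%, 60% and 70% the entries are 0.13, .0064 and 0.027.

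The statistical methods part of the synopsis prints the same table. Its row, "Probability of Failing to Observe Toxicity, N = 3", reads 0.13, 0.006 and 0.027 at those three rates.

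The text draws one worked example from Table 18, for six patients: "with 6 patients, the probability of failing to observe DLT occurring at least 40% of the time is less than 5" per cent. Table 17 gives 0.08 at a 60% rate, and the synopsis agrees.

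**The concern.** For a fixed number of patients, the chance of seeing no DLT can only fall as the true DLT rate rises. The three-patient row falls to .0064 at 60% and then rises to 0.027 at 70%, so at least one entry is wrong.

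The cell describes how well three patients screen out a very toxic dose. Under Section 4.1.1.1, no DLT in three is the result that lets escalation proceed after review of the safety data. An investigator or ethics committee reading the table would take that result to be a roughly 1 in 156 event (1/0.0064) at a 60% rate, when it is roughly 1 in 16 (1/0.064). The misprint also makes three patients look nearly as informative as six at this rate: .0064 against 0.0041, a ratio of 1.6, when the true ratio is 0.064/0.0041, about 16.

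**Working it through.** **Inputs.** Cohort sizes of 3 and 6 and true DLT rates p from 5% to 90% (Table 18); the escalation rule (Section 4.1.1.1); the printed escalation probabilities (Table 17).

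**Step 1: identify the formula.** The chance of no DLT in n patients is (1 - p)^n. The protocol's own example confirms this: 0.6^6 = 0.047 for six patients at 40%, as printed in Table 18 and below 5%.

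**Step 2: recompute Table 18.**

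| True rate | N = 3 computed | N = 3 printed | N = 6 computed | N = 6 printed |
|---|---|---|---|---|
| 5% | 0.857 | 0.86 | 0.735 | 0.74 |
| 10% | 0.729 | 0.73 | 0.531 | 0.53 |
| 20% | 0.512 | 0.51 | 0.262 | 0.26 |
| 30% | 0.343 | 0.34 | 0.118 | 0.12 |
| 40% | 0.216 | 0.22 | 0.047 | 0.047 |
| 50% | 0.125 | 0.13 | 0.016 | 0.016 |
| **60%** | **0.064** | **.0064** | 0.0041 | 0.0041 |
| 70% | 0.027 | 0.027 | 0.0007 | <0.001 |
| 80% | 0.008 | 0.008 | 0.00006 | <0.001 |
| 90% | 0.001 | 0.001 | 0.000001 | <0.001 |

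Nineteen of the 20 cells agree to the printed rounding. The exception is N = 3 at 60%, where 0.4^3 = 0.064. The printed value is low by a factor of 0.064/0.0064 = 10.0 in Table 18 and 0.064/0.006 = 10.7 in the synopsis, which is the same slip rounded to three decimals.

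**Step 3: check against Table 17.** Escalation follows 0 of 3, or 1 of 3 and then 0 of the next 3, because 2 of 6 reaches the 33% limit. Its probability is (1 - p)^3 + 3p(1 - p)^2 x (1 - p)^3. At p = 0.60:

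- 0-of-3 term: 0.064
- 1-of-3 term: 3 x 0.6 x 0.16 = 0.288
- Total: 0.064 + 0.288 x 0.064 = 0.0824, printed as 0.08

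The same formula gives 0.97, 0.91, 0.71, 0.49, 0.31, 0.17, 0.08, 0.03, 0.01 and 0.001 across the ten rates, matching every entry of Table 17. The 0-of-3 probability enters twice, so using .0064 throughout would give 0.0064 + 0.288 x 0.0064 = 0.0082, about a tenth of the printed 0.08.

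**Step 4: look for another explanation.** The six-patient value at 60% is 0.0041 and the escalation probability is 0.0824, so neither was copied into the cell by mistake. With three patients, .0064 would require a true rate of about 81%. A misplaced decimal point is the simple explanation.

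**The case against.** The strongest reply is that this is a typographical slip without consequence, and most of that stands. The worked examples in the text do not use the cell. The escalation rule is stated in counts. Section 10.1.1 requires at least six DLT-evaluable patients for the MTD, so three clean patients do not establish one. The planned maximum of 30 phase 1b patients does not rest on it either. Section 2.2.1.4 reports 18 patients already treated at the two weekly levels without DLT. The remaining tabulated level, Dose Level 3, has no higher level above it in the dose table, and at least six patients are to be treated at the every-two-week MTD or top level.

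A reader might infer that the protocol understates tenfold the risk of escalating past a very toxic dose. The documents do not support that. That risk is the Table 17 entry, which is correct at 0.08, appears in both places and already includes the 0-of-3 path. A reader might also take Table 18 to be the protocol's formal safety assurance for a three-patient cohort. The documents give it no such status, and their only example from it concerns six patients.

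What does not stand is that the slip can be dismissed as damage from reading the PDF. It appears in two tables with different rounding, and nothing elsewhere in the protocol corrects it.

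**Conclusion.** The cell is wrong in both tables. At a 60% true DLT rate, the chance that three patients show no DLT is 6.4%, not the printed 0.64% (Table 18) or 0.6% (synopsis). The only assumption is that patients' outcomes are independent with a common DLT rate, which is what the rest of Tables 17 and 18 already uses. The error is confined to this one component: the overall escalation probability is correct, and no rule, sample size or MTD definition changes. It is a minor correction, worth making because the figure is a stated operating characteristic and errs in the favourable direction.

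**What to change.** Replace .0064 with 0.064 in Table 18 (N = 3, 60% column) and 0.006 with 0.064 in the same cell of the synopsis table. No other entry in either table needs to change, nor does any design text. The cost is two edited cells and a less favourable figure at that rate.

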10.1.1.1. Definition of Analyzed Study Populations

The following study populations will be considered when reporting study results:

- The study population for safety includes all patients receiving at least a portion of 1 dose of TRC105.
- The study population for PK includes also subjects with adequate data for PK modeling of TRC105.

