In dose levels -1, 1, 2 and Expanded Cohort 1, patients will receive 800 mg of pazopanib daily p.o. in cycle 1 for two to four weeks prior to the initial dose of TRC105 on cycle 2 day 1. Dose reductions of pazopanib are allowed during this two to four week period of dosing based on individual patient tolerability. TRC105 dosing will begin at 8 mg/kg (Dose Level 1) on cycle 2 day 1. A -1 Dose Level has also been included (6 mg/kg) and will be enrolled if 8 mg/kg TRC105 dosed with pazopanib exceeds the weekly MTD. For dose levels -1, 1, 2, and Expanded Cohort 1, the DLT evaluation period, for purposes of dose expansion, will be the first 28 days of dosing pazopanib and TRC105 together (e.g., from cycle 2 day 1 through cycle 2 day 28). Each cycle will be 28 days in duration. For dose levels 3, and Expanded Cohort 2, both pazopanib and TRC105 dosing will begin on C1D1 and the DLT evaluation period will be the first 28 days of dosing pazopanib with TRC105 every 2

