3.1.3. Secondary objectives

- To assess preliminary evidence of improved antitumor activity when TRC105 is added to pazopanib, by assessing response rate and progression-free survival
- To characterize the pharmacokinetic profile of TRC105 when given with pazopanib
- To evaluate the formation of TRC105 anti-product antibodies
- To correlate efficacy with expression of endoglin on sarcoma tissue
- To explore pharmacodynamic effects on circulating angiogenic biomarkers

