5.3.5.2 Clinical Protocol

mg/kg is administered on cycle 2 day 1 and the balance (e.g., 5 mg/kg for Dose Level 1) is administered on cycle 2 day 4, the full dose is then given weekly thereafter starting with cycle 2 day 8.

^b In dose levels 3 and expanded cohort 2, pazopanib and TRC105 dosing will begin on cycle 1 day 1. Pazopanib dosing will begin on cycle 1 day 1 and once daily thereafter, and TRC105 will be administered weekly during cycle 1. The first weekly TRC105 dose will be split into two doses whereby 3 mg/kg is administered on cycle 1 day 1 and the balance is administered on cycle 1 day 4. Starting on cycle 2 day 1 and beyond, TRC105 will be administered every two weeks on days 1 and 15 once it is determined that the every two week dosing MTD has not been exceeded.

In dose levels -1, 1, 2 and expanded cohort 1, patients will receive 800 mg of pazopanib daily p.o. in cycle 1, which will be two to four weeks in duration prior to the initial dose of TRC105 given on cycle 2 day 1. Cycle 1 will therefore be as short as 14 days or as long as 28 days, based on the time needed to determine a tolerable dose of pazopanib in each patient. Dose reductions of pazopanib are allowed during cycle 1 based on individual patient tolerability (as well as following cycle 1). TRC105 dosing will begin at 8 mg/kg (Dose Level 1) on cycle 2 day 1. Prior to administration of TRC105 on cycle 2 day 1, all study patients must maintain eligibility criteria indicating adequate organ function, medical status and ECOG performance status (i.e., patients must maintain inclusion criterion #6, 8, 9 and 10 and exclusion criteria #8-21 to continue into cycle 2) and must be able to tolerate pazopanib. A -1 Dose Level has also been included (6 mg/kg) and will be enrolled if 8 mg/kg TRC105 dosed with pazopanib exceeds weekly the MTD. For dose levels -1, 1 and 2, the DLT evaluation period, for purposes of dose expansion, will be the initial 28 days of dosing with TRC105 and pazopanib (from cycle 2 day 1 through cycle 2 day 28). Each cycle will be 28 days in duration.

For dose levels 3, and Expanded Cohort 2, both pazopanib and TRC105 dosing will begin on C1D1 and the DLT evaluation will be the first 28 days of dosing pazopanib with TRC105 every 2 weeks (i.e., from cycle 2 day 1 through cycle 2 day 28). At least 6 patients will be treated at the every two week dosing MTD (or top dose level if a MTD is not determined).

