5.3.5.2 Clinical Protocol

1. RECIST 1.1-defined disease progression. In cases where RECIST cannot be applied, progression should be based on unequivocal evidence of progressive disease sufficient to require a change in therapy. In the angiosarcoma cohort 1, disease progression for withdrawal refers to disease progression while receiving TRC105 plus pazopanib combination therapy.
2. A need for surgery, radiation, or for other anticancer therapy not specified in the protocol.
3. Unable to tolerate pazopanib during cycle 1 (phase 1b, dose levels -1, 1, 2 and expanded cohort 1 only).
4. Lost to follow-up or noncompliant.
5. Any TRC105 dose delay > 2 days between cycle 2 day 1 and cycle 2 day 28 (phase 1b only).
6. Pregnancy. Pregnant patients should be followed for the duration of the pregnancy and the outcome of the pregnancy should be documented.
7. Arterial thrombosis of any grade (including cerebrovascular ischemia, cardiac ischemia/infarction, or peripheral or visceral arterial ischemia) or grade 3 or 4 venous thrombosis (including pulmonary embolism).
8. Missed study drug treatment for > 8 consecutive weeks (i.e., both TRC105 and pazopanib dosing held). However, patients who cannot tolerate pazopanib or TRC105 therapy and who demonstrate a response of complete response (CR), partial response (PR) or stable disease (SD) with the combination and are thought to benefit from continued single agent therapy may continue on study on TRC105 or pazopanib alone.

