8.3.2. Adverse Event Reporting Period

Safety information for each patient will be collected from the date of informed consent. Adverse events occurring prior to the initiation of the study treatment with pazopanib or TRC105 study drug will be considered "baseline-signs and symptoms", will be recorded on corresponding case report forms and will not be retained for patients who fail screening. The adverse event reporting period for this trial begins when the patient has received even a portion of the first dose of pazopanib or TRC105 study drug and ends 28 days after the last dose of pazopanib or TRC105 study drug is administered.

All adverse events that occur in trial patients during the adverse event reporting period specified in the protocol must be reported to TRACON, whether or not the event is considered study treatment-related. In addition, any known untoward event that occurs beyond the adverse event reporting period that the Investigator assesses as possibly related to the investigational medication/product should also be reported as an adverse event.

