5.3.5.2 Clinical Protocol

- The study population for efficacy will include all safety population patients who have baseline and follow-up tumor measurements as required for assessment by RECIST 1.1.

Patients who experience DLT who receive less than the prescribed dose of TRC105 or pazopanib due to documented toxicity in cycle 2 will be considered evaluable for dose escalation purposes.

Only those patients who are deemed "ineligible" or who receive no therapy (i.e. no TRC105 or pazopanib) will be eliminated from the analysis. Ineligible patients who receive therapy will not be included in the assessment of efficacy endpoints, but their data will be included in the assessment of all adverse event reporting.

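### For the phase 1b dose levels with a pazopanib run-in, the Section 10.1.1.1 analysis sets leave out patients lost before TRC105, against the exclusion rule in the same section

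*Combined protocol and SAP*

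**What the plan says.** The run-in applies to dose levels -1, 1, 2 and Expanded Cohort 1 and is described in the Synopsis (Methodology, Phase 1b): "patients will receive 800 mg of pazopanib daily p.o. in cycle 1 for two to four weeks prior to the initial dose of TRC105". Section 4.1.1.1 gives the length of that cycle as 14 to 28 days. Dose Level 3 and Expanded Cohort 2 start both drugs on cycle 1 day 1.

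A patient at the run-in levels can leave before TRC105 in three ways:

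- **Intolerance.** Section 5.3, criterion 3: "Unable to tolerate pazopanib during cycle 1 (phase 1b, dose levels -1, 1, 2 and expanded cohort 1 only".
- **Progression.** Section 5.3, criterion 1, which applies throughout treatment.
- **Failed re-check before cycle 2 day 1.** Section 4.1.1.1: "all study patients must maintain eligibility criteria indicating adequate organ function, medical status and ECOG performance status".

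Section 10.1.1.1 then defines the phase 1b analysis sets. For safety: "The study population for safety includes all patients receiving at least a portion of 1 dose of TRC105". The efficacy set "will include all safety population patients who have baseline and follow-up tumor measurements". The closing paragraph of that section limits removal to patients who are ineligible or "who receive no therapy (i.e. no TRC105 or pazopanib) will be eliminated from the analysis".

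Section 8.3.2 says the adverse event reporting period "begins when the patient has received even a portion of the first dose of pazopanib or TRC105 study drug". Section 10.2.1.1 counts events as treatment-emergent from initiation of treatment, and Section 14.1 requires a CRF for anyone given either drug.

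**The concern.** Pazopanib is study treatment in this protocol, yet a patient who takes it for up to four weeks and is then withdrawn is outside the safety population as defined. The plan collects that patient's adverse events, and one paragraph would keep them in the analysis. The set definition would not. The final denominator depends on which sentence the programmer follows.

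The phase 1b primary objective is safety and tolerability of TRC105 added to standard-dose pazopanib. Section 2.6.2 uses the finding that the two drugs were tolerated together to justify starting both in cycle 1 of phase 2, where there is no run-in. If patients were lost in the run-in, that inference moves from a group already shown to tolerate pazopanib to one that has not been screened in this way.

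A secondary objective (Section 3.1.3) is "To assess preliminary evidence of improved antitumor activity when TRC105 is added to pazopanib". With no control arm, a reader will set the result beside pazopanib-alone data, which have no such filter.

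**Working it through.** **1. What happens to a pazopanib-only patient under each rule (run-in levels)**

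| Rule | Pazopanib-only patient |
|---|---|
| 10.1.1.1, safety definition | Out: no TRC105 dose |
| 10.1.1.1, efficacy definition | Out: not in the safety set |
| 10.1.1.1, last paragraph | In, unless ineligible: has received pazopanib |
| 8.3.2, adverse event period | In: starts at first pazopanib dose |
| 10.2.1.1, treatment-emergent | In: onset after treatment began |
| 14.1, CRFs | In: CRF required |

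The first two rows contradict the third. It is not stated whether failing the re-check makes a patient ineligible. Even if it does, the last paragraph keeps ineligible treated patients in adverse event reporting, so the conflict over safety remains. Which criteria must be maintained also differs: the Synopsis and Section 4.1.2.2 list inclusion criteria 4, 5 and 6, whereas Sections 4.1.1.1 and 5 list 6, 8, 9 and 10. These passages need reconciling.

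**2. Which patients are affected**

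Section 2.2.1.4 reports 18 phase 1b patients treated, 3 at 8 mg/kg and 15 at 10 mg/kg weekly, which are run-in dose levels. The planned maximum is 30 (Section 10.1.1). Up to 30 - 18 = 12 patients, or 12/30 = 40%, could therefore be in cohorts with no run-in.

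**3. How many could be lost**

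The documents give no count of patients who started pazopanib and no attrition rate. If a fraction d is lost, 18 TRC105-treated patients imply 18/(1 - d) starters. The values of d below are assumptions.

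| Assumed d | Starters (rounded up) |
|---|---|
| 5% | 19 |
| 10% | 20 |
| 20% | 23 |
| 25% | 24 |

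**4. Bound on losses through progression**

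Inputs: a median PFS of 4.6 months on pazopanib (Section 2.1.1) and a run-in of 14 to 28 days. Assumption: exponential PFS. With 30.4375 days per month, 14 days is 0.46 months and 28 days is 0.92 months.

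Share with an event during the run-in = 1 - 2^(-t/4.6):

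- 14 days: 1 - 2^(-0.46/4.6) = 6.7%
- 28 days: 1 - 2^(-0.92/4.6) = 12.9%

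Table 4 schedules no scan between screening and cycle 2 day 22. Progression removes a patient from the run-in only if it is suspected and confirmed, so within this model these percentages are a ceiling for progression losses. Losses from intolerance or a failed re-check are separate and cannot be estimated.

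**The case against.** The strongest reply is that TRC105 is the investigational drug and that phase 1b asks what happens when it is added. On that view TRC105 exposure is the natural condition for analysis. For DLT evaluation this stands: the DLT window is the first 28 days of combined dosing, and Section 4.1.1.1 replaces patients who leave earlier for reasons other than DLT. The run-in is also a stated precaution (Section 2.6.1), and dose reduction is allowed during it, so intolerance need not mean withdrawal. Phase 1b activity is secondary, preliminary and descriptive, with best response listed by cohort.

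A reader might also infer three stronger things, none of which the documents support:

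- **That all phase 1b results describe run-in survivors.** Dose Level 3 and Expanded Cohort 2 have no run-in.
- **That run-in adverse events are certain to be discarded.** The last paragraph of 10.1.1.1, with Sections 8.3.2, 10.2.1.1 and 14.1, points the other way. The text is contradictory, not settled.
- **That median PFS is inflated by a known amount.** Under the exponential model, survivors' median from pazopanib start would be 4.6 + 0.46 = 5.06 to 4.6 + 0.92 = 5.52 months. That is 20% to 40% of the 6.9 - 4.6 = 2.3 month gain sought in phase 2. The arithmetic is right, but it assumes that every run-in event is recognised and leads to removal. Unrecognised progressors stay in. Phase 1b also admits prior-pazopanib patients, states no PFS time origin of its own and tests no PFS hypothesis.

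What remains is the contradiction and the missing account of treated patients who never reached TRC105.

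**Conclusion.** The point holds for dose levels -1, 1, 2 and Expanded Cohort 1. Followed as written, the safety definition leaves out patients who received study treatment and excludes their toxicity from a phase whose primary objective is tolerability. The conflict within Section 10.1.1.1 rests on the text alone and needs no modelling.

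The effect on tolerability and activity at these levels runs in the favourable direction if any patients were lost. Its size cannot be estimated from the documents. The range of 6.7% to 12.9% covers progression only and is a ceiling conditional on exponential PFS with a 4.6-month median. The DLT assessment is not called into question. This is a correction worth making, of moderate weight.

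**What to change.** In Section 10.1.1.1, define the safety population for the run-in dose levels as all patients who received any pazopanib or TRC105. That agrees with the section's last paragraph and with Sections 8.3.2 and 14.1. Carry the change into the evaluable-population statement in the Synopsis.

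Add one table by dose level showing the number who started pazopanib, the number who reached TRC105, the reasons for run-in discontinuation, and adverse events during the run-in.

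Keep the TRC105-treated set for DLT evaluation and for the main activity listing. Response among all pazopanib starters can be shown as a supplementary figure. It should not replace the main one, because it counts patients never given TRC105. A landmark PFS from cycle 2 day 1 should likewise be supplementary at most, since no scan is scheduled at that visit to confirm that patients are progression-free.

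The cost is revised wording, one extra table and slightly less favourable reported phase 1b tolerability. No new data collection is needed, because CRFs already cover every patient given pazopanib.
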